4.2 Concomitant Therapy Restrictions

4.2.1

Appropriate antibiotics, blood products, antiemetics, fluids, electrolytes and general supportive care are to be used as necessary. Antiemetics may be used per institutional guidelines. The routine use of steroids as an antiemetic is discouraged.

4.2.2 Diabetes Insipidus (DI)

Patients with DI should have monitoring of endocrine function and consultation with an endocrinologist is strongly recommended for guidance during fluid and chemotherapy administration.

For COG Supportive Care Guidelines see:

https://members.childrensoncologygroup.org/prot/reference_materials.asp under Standard Sections for Protocols.

4.3 Stratum 1 (NGGCT) Administration Guidelines for Induction

4.3.1 Cycle A (Cycles 1, 3, 5)

CARBOplatin: IV over 15-60 minutes

Day: 1

Dose: 600 mg/m²/dose

Avoid use of aluminum containing needles or administration sets.

Medication errors have occurred due to confusion between CISplatin (Platinol[®]) and CARBOplatin (PARAplatin[®]).

Etoposide: IV over 60-120 minutes

Days: 1-3

Dose: 150 mg/m²/dose

Infuse diluted solution (concentration ≤ 0.4 mg/mL) over at least 60-120 minutes; slow rate of administration if hypotension occurs. Rate should not exceed 300 mg/m²/hour (10 mg/kg/hour) (hypotension risk). The use of an in-line filter during the infusion is suggested.

Special precautions: Etoposide can be mixed in 0.9% NaCl or D₅W. Avoid use of large volumes of D₅W due to potential development of hyponatremia.

Stability: Leaching of diethylhexyl phthalate (DEHP) from PVC bags occurred with etoposide 0.4 mg/mL in 0.9% NaCl solution. To avoid leaching, prepare the etoposide solution as close as possible, preferably within 4 hours, to the time of administration or alternatively as per institutional policy. Glass or polyethylene-lined (non-PVC) containers and polyethylene-lined tubing may be used.

See the Parenteral Chemotherapy Administration Guidelines (CAG) on the COG website at: https://members.childrensoncologygroup.org/_files/disc/Pharmacy/ChemoAdminGuidelines.pdf for special precautions and suggestions for patient monitoring during the infusion. As applicable, also see the CAGs for suggestions on hydration, or hydrate according to institutional guidelines.

See Section 5.0 for Dose Modifications based on Toxicities.

The therapy delivery map (TDM) for Cycle A of Induction is on the next page.

Each cycle of Induction will begin when ANC > 1,000/ μ L and platelets > 100,000/ μ L and when off filgrastim (G-CSF) for at least 48 hours.

4.3.2 Stratum 1 NGGCT Cycle A Induction Induction consists of six cycles (Cycle A and Cycle B). Cycle A is given during Cycles 1, 3 and 5. This Cycle lasts 3 weeks (21 days).
	_____ Patient name or initials _____ _____ DOB
---	--

Criteria to start this cycle: ANC > 1,000/ μ L and platelets > 100,000/ μ L and off filgrastim (G-CSF) for at least 48 hours. Extensive details are in [Section 4.0](#) (treatment overview). This cycle lasts 21 days and the TDM for this cycle is on **1** page.

DRUG	ROUTE	DOSAGE	DAYS	IMPORTANT NOTES	OBSERVATIONS
CARBOplatin (CARBO)	IV over 15-60 minutes	600 mg/m ² /dose	1	See Section 5.1.1 if renal function is abnormal.	a. History, PE (Ht, Wt, VS) with Neurologic Exam, Performance Status b. CBC (differential, platelets) c. Urinalysis
Etoposide (ETOP)	IV over 60-120 minutes	150 mg/m ² dose	1-3	See admin guidelines in Section 4.3.1	d. Electrolytes (including BUN, Calcium, PO ₄ , Magnesium, Sodium, Potassium) e. Total protein, AST, ALT, albumin, bilirubin OBTAIN OTHER STUDIES AS REQUIRED FOR GOOD PATIENT CARE

Enter Cycle #: _____ Ht _____ cm Wt _____ kg BSA _____ m²

Date Due	Date Given	Day	CARBO mg	ETOP mg	Studies	Comments (Include any held doses, or dose modifications)
			Enter calculated dose above and actual dose administered below			
		1	_____ mg	_____ mg	a, b, c, d, e	
		2		_____ mg		
		3		_____ mg		
		4				
		8			b, d [@]	
		15			b, d [@]	
		22	Start Cycle B on Day 22 or when blood count parameters are met (whichever occurs later).			

@ Obtain weekly if clinically indicated.

See [Section 5.0](#) for Dose Modifications for Toxicities and the COG website posted materials for Supportive Care Guidelines.

4.3.3 Cycle B (Cycles 2, 4, 6)

Ifosfamide: IV over 60 minutes

Days: 1-5

Dose: 1800 mg/m²/dose

Suggested hydration: Administer 3,000 mL/m²/day (125 mL/m²/hour) using fluid containing D₅W/0.45% NaCl or 0.9% NaCl. Achieve urine specific gravity ≤ 1.010 prior to start of ifosfamide. Monitor for adequate urine output as per institution guidelines. May use diuretics (eg, furosemide) to increase urine output. Consider adding potassium and magnesium to prevent electrolyte deficiencies.

Etoposide: IV over 60-120 minutes*

Days: 1-5

Dose: 100 mg/m²/dose

Note: Infuse as diluted solution (concentration ≤ 0.4 mg/mL); *slow rate of administration if hypotension occurs. Rate should not exceed 300 mg/m²/hour (10 mg/kg/hour) (hypotension risk). The use of an in-line filter during the infusion is suggested.

Special precautions: Etoposide can be mixed in 0.9% NaCl or D₅W. Avoid use of large volumes of D₅W due to potential development of hyponatremia.

Mesna: IV (short or continuous infusion)

Days: 1-5

Total Dose: 1800 mg/m²/day

IV short or continuous infusion: For prophylaxis of hemorrhagic cystitis, the total daily mesna dose is equal to 100% of the daily ifosfamide dose. Mesna can be administered in 5 divided doses by **short intravenous infusion** over 15 to 30 minutes. The initial bolus dose of mesna may be administered 15 minutes before or at the same time as the ifosfamide dose; subsequent doses are given 3, 6, 9, and 12 hours after the start of ifosfamide.

For example: if the ifosfamide dose is 1000 mg, then the total daily mesna dose is 1000 mg; 200 mg of mesna will be given 15 minutes before or with the ifosfamide dose (Hour 0) and 4 boluses of 200 mg each will be given at Hours 3, 6, 9 and 12.

This total daily dose of mesna can also be administered as IV **continuous infusion**. The continuous infusion should be started 15-30 minutes before or at the same time as ifosfamide and finished no sooner than 12 hours after the end of the ifosfamide infusion.

For example: if the ifosfamide dose is 1000 mg, then the total daily mesna dose is 1000 mg; the 1000 mg mesna continuous infusion will start 15-30 minutes before or at the same time as the ifosfamide and be completed no sooner than 12 hours after **the end** of the ifosfamide infusion. If ifosfamide is administered over 2 hour and mesna is started 30 minutes before the ifosfamide infusion, the total mesna infusion will last at least 14 hours and 30 minutes.

Use of oral mesna:

The oral dose of mesna is **twice** the IV dose. Patients able to tolerate oral mesna may receive the last **FOUR** bolus doses (originally at Hours 3, 6, 9, and 12) orally at 40% of the ifosfamide dose. The oral doses will be administered at Hours 1, 4, 7, and 10.

For example: if the ifosfamide dose is 1000 mg, then the first 200 mg dose of mesna will be given IV 15 minutes before or with the ifosfamide dose (Hour 0) and **FOUR** oral doses of 400 mg each will be given at Hours 1, 4, 7, and 10.

Administer tablets or diluted parenteral solution. To decrease sulfur odor, dilute mesna parenteral solution before oral administration. The solution can be diluted 1:1 to 1:10 in water, carbonated cola drinks, fruit juices (grape, apple, tomato and orange) or plain or chocolate milk. The most palatable is chilled grape juice. Tablets are 400 mg each and can be divided into 200 mg/0.5 tabs so dosing can be rounded up to nearest 200mg. Administer doses on a schedule as determined by timing of ifosfamide administration. If a dose is missed, administer dose immediately. Give the next scheduled dose according to the original dosing schedule. Do not deviate from the original schedule. Notify provider if a dose is delayed or missed. If a dose is vomited within 2 hours of administration, repeat the dose orally or switch to intravenous mesna.

Filgrastim: Subcutaneous (preferred) or IV

Days: Daily, starting on Day 6 and continue for 10 days until ANC > 1500/ μ L after the expected nadir.

Dose: 5 mcg/kg/dose.

Note: The use of filgrastim is strongly recommended, however, patients receiving PEG-filgrastim will not be excluded.

See the Parenteral Chemotherapy Administration Guidelines (CAG) on the COG website at: https://members.childrensoncologygroup.org/_files/disc/Pharmacy/ChemoAdminGuidelines.pdf for special precautions and suggestions for patient monitoring during the infusion. As applicable, also see the CAGs for suggestions on hydration, or hydrate according to institutional guidelines.

See [Section 5.0](#) for Dose Modifications based on Toxicities.

The therapy delivery map (TDMs) for Cycle B of Induction is on the next page.

Each cycle of Induction will begin when ANC > 1,000/ μ L and platelets > 100,000/ μ L and when off of filgrastim (G-CSF) for at least 48 hours.


4.3.4 Stratum 1 NGGCT Cycle B Induction Induction consists of six cycles (Cycle A and Cycle B). Cycle B is given during Cycles 2, 4 and 6. This Cycle lasts 3 weeks (21 days).
	
_____
 
Patient name or initials
 
_____
 
DOB

---	--

Criteria to start this cycle: ANC > 1,000/ μ L and platelets > 100,000/ μ L and off filgrastim (G-CSF) for at least 48 hours. Extensive details are in [Section 4.0](#) (treatment overview). This cycle lasts 21 days and the TDM for this cycle is on 1 page.

DRUG	ROUTE	DOSAGE	DAYS	IMPORTANT NOTES	OBSERVATIONS
Ifosfamide (IFOS)	IV over 60 minutes	1800 mg/m ² /dose	1-5	See admin guidelines in Section 4.3.3	a. History, PE (Ht, Wt, VS) with Neurologic Exam, Performance Status b. CBC (differential, platelets) c. Urinalysis d. Electrolytes (including BUN, Calcium, PO ₄ , Magnesium, Sodium, Potassium) e. Serum Creatinine, CrCl or GFR f. Total protein, AST, ALT, albumin, bilirubin g. Lumbar CSF cytology* h. Lumbar CSF Markers (hCG, AFP)* i. Serum Markers (hCG, AFP) j. Brain MRI with and without gadolinium k. Spine MRI with and without gadolinium l. Audiogram or BAER m. Endocrine function * Lumbar CSF should be obtained unless medically contraindicated. OBTAIN OTHER STUDIES AS REQUIRED FOR GOOD PATIENT CARE
Etoposide (ETOP)	IV over 60-120 minutes	100 mg/m ² /dose	1-5	See admin guidelines in Section 4.3.3	
Mesna (MESNA)	IV (short or continuous infusion)	See Section 4.3.3	1-5	Administer concurrently with ifosfamide	
Filgrastim (G-CSF)	SubQ (preferred) or IV	5 mcg/kg/dose	Daily on Days 6-15	Start G-CSF on Day 6 and continue for ten days or until ANC > 1500/ μ L.	

Enter Cycle #: _____ Ht _____ cm Wt _____ kg BSA _____ m²

Date Due	Date Given	Day	IFOS _____mg	ETOP _____mg	MESNA _____mg	G-CSF _____mcg	Studies	Comments (Include any held doses, or dose modifications)	
			Enter calculated dose above and actual dose administered below						
		1	_____mg	_____mg	_____mg		a, b, c, d, e, f		
		2	_____mg	_____mg	_____mg				
		3	_____mg	_____mg	_____mg				
		4	_____mg	_____mg	_____mg				
		5	_____mg	_____mg	_____mg				
		6				_____mg			
		8					b, d@		
		15					b, d@		
		21					I\$, j\$ [a,b,c,d,e,f,g, h,i,j,k,l,m]#	Indicate date of last G-CSF dose _____	
		22	Start Cycle A on Day 22 or when blood count parameters are met (whichever occurs later). Upon completion of Induction, patients will undergo response evaluation.						

\$ Obtain after cycles 2 and 4

@ Obtain weekly if clinically indicated.

Obtain at completion of Induction (after Cycle 6).

See [Section 5.0](#) for Dose Modifications for Toxicities and the COG website posted materials for Supportive Care Guidelines.

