4.1 Overview of Treatment Plan

Induction Chemotherapy

All patients must begin therapy within 31 days of definitive diagnostic surgery or clinical diagnosis and 5 calendar days from enrollment on study. Each subsequent cycle of Induction chemotherapy will begin when ANC > 1,000/ μ L and platelets > 100,000/ μ L and when off filgrastim (G-CSF) for at least 48 hours (if applicable).

Cycle A: (21 Days)

Carboplatin (600 mg/m²/dose) Day 1
Etoposide (150 mg/m²/dose) Days 1-3

Cycle B: (21 Days)

Ifosfamide (1800 mg/m²/dose) Days 1-5
Etoposide (100 mg/m²/dose) Days 1-5
Mesna (1800mg/m²/day) Days 1-5
Filgrastim (G-CSF) (5 micrograms/kg/day) Days 6-15 or until ANC > 1500/ μ L

Growing Teratoma Syndrome

Second-look surgery is strongly recommended in patients with normalization of markers who fail to achieve a radiographic CR or PR to induction chemotherapy and in patients with increasing size of the mass on MRI scan and negative markers at any time during Induction chemotherapy. If a mature teratoma and/or fibrosis are removed, the patient remains on protocol and should continue therapy as planned. Response should be assessed according to the radiographic and tumor marker response criteria listed in [Section 10](#).

Chemotherapy for NGGCT (Stratum 1)

Week								
0	3	Evaluation	6	9	Evaluation	12	15	Response Evaluation
Cycle A	Cycle B	(MRI/tumor markers)	Cycle A	Cycle B	(MRI/tumor markers)	Cycle A	Cycle B	(MRI/tumor markers)

Patients will receive 6 cycles of induction chemotherapy consisting of carboplatin and etoposide (Cycles 1, 3, and 5) alternating with ifosfamide and etoposide (Cycles 2, 4, and 6). The entire length of Induction is approximately 18 weeks unless delay occurs due to myelosuppression or unanticipated toxicity.

Following induction chemotherapy, those patients in CR or PR will undergo radiation therapy 30.6 Gy WVI with IFR boost to 54 Gy in 1.8 Gy daily fractions.

For those patients with PR, SD or PD and normalization of tumor marker levels in serum and CSF, second-look surgery is strongly recommended. Patients who achieve CR/PR via second-look surgery (and have histology consistent with fibrosis, scar or mature teratoma) will then proceed to radiation therapy as above.

Patients with positive markers or who have < PR after induction chemotherapy/second-look surgery will be removed from protocol therapy.

Patients with residual viable malignant elements (except mature teratoma) on second-look surgery will be removed from protocol therapy.

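### The Cycle B filgrastim instructions are inconsistent: the delivery map changes unit from mcg to mg, and Section 4.3.3 states a different stopping rule from Sections 4.1 and 4.3.4

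*Combined protocol and SAP*

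**What the plan says.** Filgrastim in Cycle B (Cycles 2, 4 and 6 of Stratum 1) is described in three places.

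- **Section 4.1**, treatment overview: "Filgrastim (G-CSF) (5 micrograms/kg/day) Days 6-15 or until ANC" exceeds 1500/µL.
- **Section 4.3.3**, administration guideline: "Daily, starting on Day 6 and continue for 10 days until ANC" exceeds 1500/µL, with the qualifier "after the expected nadir". The dose is given as "Dose: 5 mcg/kg/dose".
- **Section 4.3.4**, therapy delivery map, notes column: "Start G-CSF on Day 6 and continue for ten days or until ANC" exceeds 1500/µL. The map's drug table repeats 5 mcg/kg per dose and gives Days 6-15.

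The lower part of the map is a form that carries the instruction "Enter calculated dose above and actual dose administered below". The blank in the G-CSF column heading, for the calculated dose, is in mcg. The blank on the Day 6 row, for the dose given, is in mg. The ifosfamide, etoposide and mesna columns use mg in both positions.

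Section 4.3.3 strongly recommends filgrastim but does not exclude patients who receive PEG-filgrastim.

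**The concern.** These are operative treatment instructions and a dosing form, not background text. Two sites can each follow a page of the same protocol and act differently on the same blood count. One works from the guideline page, which has a nadir condition. The other works from the map, which has none.

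The change of unit between two blanks in the same column invites a transcription error on a form used for children. The number entered in the heading is the natural one to copy to the row below, and the printed unit there is different.

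What is at stake is consistent supportive care and a clear dose entry on the map. The stopping day also bears on when the next cycle can begin, because each induction cycle requires ANC above 1,000/µL, platelets above 100,000/µL and at least 48 hours off filgrastim.

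**Working it through.** The plan gives no calculated figure to reproduce here. The check is a side-by-side reading, a unit conversion and a day count.

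**1. What agrees.** All three sections give 5 micrograms/kg daily, a Day 6 start and an ANC threshold of 1500/µL. Days 6 to 15 inclusive is 15 − 6 + 1 = 10 days, so the day range in Section 4.1 and the ten days in Sections 4.3.3 and 4.3.4 are the same length.

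**2. Unit on the map.** The mg blank is the only entry on the Day 6 row and stands in the G-CSF position. The other three drugs end on Day 5, so it cannot belong to one of them.

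- Conversion: 1 mg = 1000 mcg.
- Assumed weight 30 kg (not in the documents): 5 × 30 = 150 mcg = 0.15 mg.
- Assumed range 15 to 70 kg: 5 × 15 = 75 mcg to 5 × 70 = 350 mcg, that is 0.075 to 0.35 mg.
- The same digits copied from the heading to the Day 6 line would read 75 to 350 mg, a factor of 1000 at any weight.

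**3. Stopping rule.** Here the alternative in Sections 4.1 and 4.3.4 is read as whichever comes first, which fits the map's limit of Days 6-15.

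| Situation | Sections 4.1 and 4.3.4 | Section 4.3.3 |
|---|---|---|
| ANC > 1500/µL before the expected nadir | Stopping permitted | Criterion not met |
| ANC > 1500/µL after the nadir, before Day 15 | Stopping permitted | Unclear whether the ten days must still be completed |
| ANC ≤ 1500/µL after ten days | Treatment ends | Unclear: ten days may be a fixed length, a cap, or secondary to the ANC |

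**4. When the difference can arise.** Section 7.1 asks for a weekly blood count during induction, and the map places it on Days 8 and 15. The first scheduled ANC after filgrastim starts is therefore on Day 8. By then two doses (Days 6 and 7) have been given, or three if Day 8 is included. A stop on that count leaves 10 − 2 = 8 or 10 − 3 = 7 of the ten days untreated under Sections 4.1 and 4.3.4. Under Section 4.3.3 the same pre-nadir count would not permit the stop.

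**The case against.** Several stronger readings are tempting, and the documents do not support them.

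- **Two prescribed doses.** A reader might infer that the map prescribes in both mcg and mg. It does not. The dose is in micrograms in Sections 4.1 and 4.3.3, in the map's drug table and in the heading for the calculated dose. The mg stands only beside a blank for recording. The table was read by a program, so a lost letter cannot be wholly excluded, although the row's layout makes that unlikely.
- **A damaged trial dose record.** The map has one G-CSF dose line for a drug given daily, but it also asks for the date of the last G-CSF dose and has a column for held or modified doses. The case report forms are posted separately (Section 12.0) and are not in the documents. Daily entry lines would be a preference, and loss of dose data is not shown.
- **A ten-day difference between the rules.** Stopping on Day 6 would need an unscheduled count. On scheduled counts the early-stop difference is 7 to 8 days. If Section 4.3.3 has no cap, ten days is not an upper bound either.
- **Every Stratum 1 patient affected.** PEG-filgrastim is allowed, and patients may leave protocol therapy during induction. The roughly 125 planned patients are a ceiling, not a count of those exposed.
- **Loss of patients from the primary analysis set.** Early stopping might slow recovery and so breach the six-week limit for starting radiotherapy in Section 8.1(m). That limit runs from Day 1 of the last induction cycle, so only Cycle 6 could matter. The numerical ANC gate is written for chemotherapy cycles; for starting radiotherapy, Section 15.2.3 speaks only of recovery. The documents give no frequency, so this route is speculation.

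What stands after these objections is the conflict in the text itself: the units on the map, and the stopping rule of Section 4.3.3 against the other two sections.

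**Conclusion.** The concern holds as an internal inconsistency in treatment instructions, with two parts.

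1. The heading and the administered-dose line of one column on the Cycle B map differ in unit by a factor of 1000. This is a recording or transcription hazard. The prescribed dose is not in doubt.
2. Section 4.3.3 differs from Sections 4.1 and 4.3.4 by a missing alternative and an added nadir condition. The sections lead to different actions on a pre-nadir ANC above 1500/µL, realistically at the Day 8 count, and Section 4.3.3 does not settle what to do when the ANC is still at or below 1500/µL after ten days.

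The scope is Stratum 1 patients given daily filgrastim in Cycles 2, 4 and 6. How often the conflict would change what is done cannot be estimated from the documents. No effect on sample size, error rates or the primary analysis is shown. The verdict rests on the map's units having been read correctly from the table, and on reading the alternative in Sections 4.1 and 4.3.4 as whichever comes first. It takes no view on which unit or stopping rule is right. The correction should be made because the text bears on patient safety and is cheap to change.

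**What to change.** The sponsor should:

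- check the mg entry against the typeset map in Section 4.3.4, and reconcile the units used in the G-CSF column so that heading and entry line agree;
- reconcile the stopping statements in Sections 4.1, 4.3.3 and 4.3.4 into one rule chosen by the clinical team and worded identically in all three places. It should say whether a nadir condition applies, how the ten days relate to the ANC criterion, and what is done if the ANC is still at or below 1500/µL after ten days.

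The cost is a correction to one form and to the stopping sentences, plus notice to sites. Nothing in the statistical section needs to change.

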4.4 Stratum 2 (Germinoma) Administration Guidelines for Induction

4.4.1 Cycle A (Cycles 1-4)

CARBOplatin: IV over 15-60 minutes

Day: 1

Dose: 600 mg/m²/dose

IV: Infuse the diluted solution over 15-60 minutes. Avoid use of aluminum containing needles or administration sets.

Medication errors have occurred due to confusion between CISplatin (Platinol[®]) and CARBOplatin (PARAplatin[®]).

Etoposide: IV over 60-120 minutes

Days: 1-3

Dose: 150 mg/m²/dose

Infuse diluted solution (concentration ≤ 0.4 mg/mL) over at least 60-120 minutes; slow rate of administration if hypotension occurs. Rate should not exceed 300 mg/m²/hour (10 mg/kg/hour) (hypotension risk). The use of an in-line filter during the infusion is suggested.

Special precautions: Etoposide can be mixed in 0.9% NaCl or D₅W. Avoid use of large volumes of D₅W due to potential development of hyponatremia.

Stability: Leaching of diethylhexyl phthalate (DEHP) from PVC bags occurred with etoposide 0.4 mg/mL in 0.9% NaCl solution. To avoid leaching, prepare the etoposide solution as close as possible, preferably within 4 hours, to the time of administration or alternatively as per institutional policy. Glass or polyethylene-lined (non-PVC) containers and polyethylene-lined tubing may be used.

See the Parenteral Chemotherapy Administration Guidelines (CAG) on the COG website at:

https://members.childrensoncologygroup.org/_files/disc/Pharmacy/ChemoAdminGuidelines.pdf for special precautions and suggestions for patient monitoring during the infusion. As applicable, also see the CAGs for suggestions on hydration, or hydrate according to institutional guidelines.

See [Section 5.0](#) for Dose Modifications based on Toxicities.

The therapy delivery map (TDM) for Cycle A of Induction is on the next page.

Each cycle of Induction will begin when ANC > 1,000/ μ L and platelets > 100,000/ μ L and when off filgrastim (G-CSF) for at least 48 hours.

4.4.2 Stratum 2 Germinoma Cycle A Induction Induction consists of four cycles. Cycle A is given in all four cycles. This Cycle lasts 3 weeks (21 days).
	
_____
 
Patient name or initials
 
_____
 
DOB

--	--

Criteria to start this cycle: ANC > 1,000/ μ L and platelets > 100,000/ μ L and off filgrastim (G-CSF) for at least 48 hours. Extensive details are in Section 4.0 (treatment overview). This cycle lasts 21 days and the TDM for this cycle is on **1** page.

DRUG	ROUTE	DOSAGE	DAYS	IMPORTANT NOTES	OBSERVATIONS
CARBOplatin (CARBO)	IV over 15-60 minutes	600 mg/m ² /dose	1	See Section 5.1.1 if renal function is abnormal.	a. History, PE (Ht, Wt, VS) with Neurologic Exam, Performance Status b. CBC (differential, platelets) c. Urinalysis
Etoposide (ETOP)	IV over 60-120 minutes	150 mg/m ² /dose	1-3	See admin guidelines in Section 4.4.1	d. Electrolytes (including BUN, Calcium, PO ₄ , Magnesium, Sodium, Potassium) e. Serum Creatinine, CrCl or GFR f. Total protein, AST, ALT, albumin, bilirubin g. Lumbar CSF cytology* h. Lumbar CSF Markers (hCG, AFP)* i. Serum Markers (hCG, AFP) j. Brain MRI with and without gadolinium k. Spine MRI with and without gadolinium l. Audiogram or BAER m. Endocrine function * Lumbar CSF should be obtained unless medically contraindicated. OBTAIN OTHER STUDIES AS REQUIRED FOR GOOD PATIENT CARE

Enter Cycle #: _____ Ht _____ cm Wt _____ kg BSA _____ m²

Date Due	Date Given	Day	CARBO mg	ETOP mg	Studies	Comments (Include any held doses, or dose modifications)
			Enter calculated dose above and actual dose administered below			
		1	_____ mg	_____ mg	a, b, c, d, f	
		2		_____ mg		
		3		_____ mg		
		4				
		8			b, d@	
		15			b, d@	
		21			i [§] , j [§] [a,b,c,d,e,f,g,h,i,j,k,l,m]#	
		22	Start next cycle on Day 22 or when blood count parameters are met (whichever occurs later). Upon completion of Induction, patients will undergo response evaluation.			

§ Obtain after Cycle 2.

@ Obtain weekly if clinically indicated

Obtain at completion of Induction (after Cycle 4).

See [Section 5.0](#) for Dose Modifications for Toxicities and the COG website posted materials for Supportive Care Guidelines.

